24.3 Safety Analyses

HCT is a complex procedure with varying causes of death post HCT. Patients may die of relapse or progression of disease, development or worsening of acute GVHD after exposure to study drug, development or worsening of chronic GVHD after exposure to study drug, infections in absence of GVHD or other causes (other non-relapse mortality) (includes drug adverse effects).

Both cohort A and B will be at risk for these events and thus will be included in the safety analyses.

In order to safeguard patients, we have set the following limits:

- Development of grade 3-4 acute GVHD by day 180 post HCT for patients who have no acute GVHD prior to starting experimental therapy should not be higher than 30%.
- Development of grade 3-4 acute GVHD for patients with grade 1-2 acute GVHD prior to starting experimental therapy should not be higher than 40%.
- Development of grade 3-4 acute GVHD for patients with any grade acute GVHD prior to starting experimental therapy should not be higher than 50%.
- Cumulative incidence of infectious disease mortality (not related to GVHD) should not be higher than 30% at 1 y post HCT
- Cumulative incidence of non-relapse mortality (all cause) at 1 y post HCT should not be higher than 40%

Stopping Rules

Cohort B is an exploratory cohort of 10 patients with diagnoses of follicular lymphoma or Hodgkin disease. Combining cohort, A and B with 75 patients in total, the stopping rules are created based on Bayesian approach to monitor treatment related AEs defined below during the conduct of a clinical trial. We will stop the trial early if the probability that treatment related events of the current regimen exceeds conventional treatment related AE is greater than 80%.

The following tables describe the safety rules. There will be 2 conference calls per month during the conduct of the study to ensure the implementation of the safety rules.

Development of grade 3-4 acute GVHD by day 180 post HCT for patients who have no acute GVHD prior to starting experimental therapy should not be higher than 30%.

Number of patients in complete cohorts of 5 (inclusive)	Stop the trial if this number of toxicities (inclusive)
5	3
10	5
15	7
20	8
25	10
30	12

Development of grade 3-4 acute GVHD for patients with grade 1-2 acute GVHD prior to starting experimental therapy should not be higher than 40%.

Number of patients in complete cohorts of 5 (inclusive)	Stop the trial if this number of toxicities (inclusive)
5	4
10	6
15	8
20	10
25	13
30	15
35	17
40	19

Development of grade 3-4 acute GVHD for patients with any grade acute GVHD prior to starting experimental therapy should not be higher than 50%.

Number of patients in complete cohorts of 5 (inclusive)	Stop the trial if this number of toxicities (inclusive)
5	4
10	6
15	8
20	10
25	13
30	15
35	17
40	19

Cumulative incidence of infectious disease mortality (not related to GVHD) should not be higher than 30% at 1 y post HCT.

Number of patients in complete cohorts of 5 (inclusive)	Stop the trial if this number of toxicities (inclusive)
5	4
10	6
15	8
20	10
25	13
30	15
35	17
40	19

Cumulative incidence of non-relapse mortality (all cause) at 1 y post HCT should not be higher than 40%.

Number of patients in complete cohorts of 5 (inclusive)	Stop the trial if this number of toxicities (inclusive)
5	4
10	6
15	8
20	10
25	13
30	15
35	17
40	19

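### One stopping boundary, which fits only a 40% limit, is also printed under the 30% infectious-death limit and the 50% GVHD limit, so the infectious-death rule is redundant

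*Combined protocol and SAP*

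**What the plan says.** Section 24.3 (Safety Analyses) sets five limits and one criterion. The trial stops "if the probability that treatment related events of the current regimen exceeds conventional treatment related AE is greater than 80" per cent. The method is described as Bayesian, and no prior is given. The five limits and their printed boundaries, read every 5 patients, are:

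| Rule | Limit | Events that stop the trial at n = 5, 10, 15, … |
|---|---|---|
| Grade 3–4 acute GVHD, no prior acute GVHD | 30% | 3, 5, 7, 8, 10, 12 (to n = 30) |
| Grade 3–4 acute GVHD, prior grade 1–2 | 40% | 4, 6, 8, 10, 13, 15, 17, 19 (to n = 40) |
| Grade 3–4 acute GVHD, prior acute GVHD of any grade | 50% | same as the row above |
| Infectious death not related to GVHD, 1 year | 30% | same |
| Non-relapse mortality, all cause, 1 year | 40% | same |

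The wording of the last three limits is "Development of grade 3-4 acute GVHD for patients with any grade acute GVHD prior to starting experimental therapy should not be higher than 50" per cent, "Cumulative incidence of infectious disease mortality (not related to GVHD) should not be higher than 30% at 1 y post HCT", and "Cumulative incidence of non-relapse mortality (all cause) at 1 y post HCT should not be higher than 40" per cent. The opening paragraph of 24.3 lists, among causes of death other than relapse, "infections in absence of GVHD or other causes (other non-relapse mortality". The monitored population is described as "Combining cohort, A and B with 75 patients in total".

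**The concern.** A single criterion cannot give the same boundary for limits of 30%, 40% and 50%, nor two different boundaries for the same 30% limit. The section gives no reason for either. These are operating rules that decide whether the trial continues. At 15 infectious deaths among 40 patients, someone applying the stated criterion to the 30% limit would stop and someone reading the table would not.

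Two consequences need sizing. The separate safeguard against infectious death may do no work as tabulated. The 50% GVHD table may stop the trial at a rate that its own limit treats as acceptable.

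**Working it through.** **Inputs (all from 24.3).** The five limits, the printed boundaries, the 80% criterion, and looks every 5 patients. The prior is not stated. I assume a beta prior centred on the limit L with weight w, and vary w over 1, 1.5 and 2.

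**Formula.** With x events in n patients, the posterior is Beta(wL + x, w(1 − L) + n − x). The boundary at n is the smallest x with P(rate > L) > 0.80.

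**Reproducing the plan's own tables.** For every w:

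- L = 0.30 gives 3, 5, 7, 8, 10, 12 at n = 5 to 30, which is the printed first GVHD table (all six rows).
- L = 0.40 gives 4, 6, 8, 10, 13, 15, 17, 19, which is the repeated table (all eight rows).

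So the method is recovered and the repeated table is a 40% table. Scanning limits from 0.30 to 0.545 in steps of 0.005, only 0.395 and 0.40 reproduce it. A wider grid of beta priors (both parameters 0.1 to 20) found many that fit it at 40% and none at 30%, 35%, 45% or 50%.

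**Posterior at the printed boundary (w = 1).**

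| n | Printed x | Observed rate | P(rate > 30%) | P(rate > 50%) |
|---|---|---|---|---|
| 5 | 4 | 80% | 0.98 | 0.91 |
| 10 | 6 | 60% | 0.97 | 0.74 |
| 15 | 8 | 53% | 0.96 | 0.60 |
| 20 | 10 | 50% | 0.96 | 0.50 |
| 25 | 13 | 52% | 0.99 | 0.58 |
| 30 | 15 | 50% | 0.99 | 0.50 |
| 35 | 17 | 48.6% | 0.99 | 0.43 |
| 40 | 19 | 47.5% | 0.99 | 0.38 |

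Against 30% the table waits for far more certainty than 80% at every look. Against 50% it meets the criterion only at n = 5.

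**Boundaries that match the limits, n = 5 to 40.**

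- 30%: 3, 5, 7, 8, 10, 12, 13, 15.
- 50%: 4, 7, 10, 12, 15, 18, 20 (21 for w = 1.5 or 2), 23.

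Uniform and Jeffreys priors do not reproduce the undisputed tables exactly, but they also give 15/40 and 23/40. The discrepancy at n = 40 is therefore the same under all five priors.

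**Redundancy.** On the same patients, non-relapse deaths = infectious deaths + other non-relapse deaths ≥ infectious deaths. With equal thresholds at every look, any count that crosses the infectious-death boundary also crosses the non-relapse mortality boundary.

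**Stopping probability by n = 40, mortality rules** (independent binary outcomes, exact recursion). Taken alone at a true infectious-death rate of 40%, the printed table stops with probability 41% and the matched table with 82%. The trial also runs the non-relapse mortality rule, so the fairer comparison has both in force:

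| Infectious death | Other non-relapse mortality (assumed) | As printed | Matched 30% table | Difference |
|---|---|---|---|---|
| 35% | 5% | 41% | 65% | 24 |
| 35% | 10% | 62% | 73% | 11 |
| 35% | 15% | 81% | 84% | 3 |
| 40% | 5% | 62% | 83% | 21 |
| 40% | 10% | 81% | 88% | 7 |
| 40% | 15% | 93% | 94% | about 2 (92.6 vs 94.5) |

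**50% GVHD rule, taken alone, true rate 40%.** Printed versus matched: 34% versus 14% by n = 20, 37% versus 15% by n = 30, and 41% versus 15–16% by n = 40.

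**The case against.** The strongest reply accepts the contradiction and disputes its size.

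- **The 41% versus 82% contrast is not the trial-level effect.** Correct. With the non-relapse mortality rule in force, the loss is the 2 to 24 points tabulated above.
- **The GVHD effect shrinks once the overlapping rule is counted.** Patients with any prior acute GVHD include those with grade 1–2, whose 40% rule remains. At a true 40% rate, simulating both rules over 40 such patients with 50–100% of them grade 1–2 (an assumption; the documents do not give the share), correction changes the stopping probability by 0 to 13 points, not about 25. This stands. The error is also in the cautious direction, so this half is an inconsistency to reconcile rather than a safety gap.
- **Redundancy needs both rules to count the same deaths.** Whether an infectious death after relapse counts as non-relapse mortality is not defined, and Section 21.1 leaves room to continue ibrutinib after relapse. The claim therefore holds for infectious deaths counted as non-relapse deaths in the same patients, under the printed tables.
- **Other oversight exists.** Every death is reported as a serious adverse event, the data and safety monitoring committee reviews these events quarterly, and there are two calls a month. None of this corrects a wrong table.
- **Rows beyond 40 patients are a lesser matter.** With 1-year outcomes and two-year accrual, those rows may come too late to halt enrolment, though they could still affect patients on drug. The point is secondary, and the main finding does not depend on it.

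**Conclusion.** The concern holds. The repeated boundary is a 40% boundary. Under the 30% infectious-death limit it is too permissive at every look and contradicts the section's other 30% table. Under the 50% GVHD limit it stops too readily from n = 10 on, and at n = 35 and 40 below the limit itself. As tabulated, infectious death has no effective boundary of its own: mortality is monitored at the 40% non-relapse limit only.

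The cost is about 2 to 24 points of stopping probability by 40 patients at infectious-death rates of 35–40%. That range assumes independent binary outcomes, a look every 5 patients and other non-relapse mortality of 5–15%. The prior is inferred, but 15/40 and 23/40 against the printed 19/40 hold under all five priors compared. The size of the any-grade GVHD subgroup is not given.

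This must be fixed, because operative stopping thresholds contradict the limits that they are meant to enforce.

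**What to change.** Reconcile the limits with the tables by protocol amendment. Either regenerate the infectious-death and any-grade GVHD tables from their stated limits, or restate those limits if the printed boundaries were intended. The choice of limit is the sponsor's. State the prior in either case.

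If the limits stand, a limit-centred prior of weight 1–2 gives the 30% and 50% boundaries shown in the check. Because the criterion is written for 75 patients and the two mortality tables end at 40, extend both. At n = 45 to 75 a 30% limit continues 17, 18, 20, 22, 23, 25, 27 and a 40% limit continues 21, 24, 26, 28, 30, 32, 34. Say also which patients count as evaluable at each look, and whether infectious deaths after relapse count as non-relapse mortality.

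The cost is two replaced tables and some added rows, with no extra patients or data. There is a price to weigh first. Taken alone, the regenerated 30% table stops by n = 40 with probability 42% at a true rate of exactly 30% (printed 11%) and 22% at a true rate of 25% (printed 4%), rising to 48% and 24% if run to 75. With the non-relapse mortality rule in force and other non-relapse mortality at 5–15%, the figures by n = 40 are 43–67% (printed 23–62%) at 30% and 24–45% (printed 11–41%) at 25%. If that is more early stopping than the sponsor wants, the limit or the 80% criterion should be changed openly.

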24.2 Sample Size

The following table reflects the power and effect size, if we enroll 65 patients with varying proportion of the diagnoses. **These calculations are based on the maximum likelihood estimator (MLE) for the mean survival time assuming exponentially-distributed PFS⁵³ using the cube-root transformation of the MLE as suggested by Spratt⁵⁴. The one-year survival probability can be calculated once the distribution is specified.** The following test statistic has a standard normal distribution:

$$\frac{\hat{\phi} - \phi}{(\hat{\phi}^2/9\hat{Q})^{1/3}} \sim N(0,1),$$

where $\hat{\phi} = \hat{\theta}^{-1/3}$, $\hat{\theta}$ is the MLE for the PFS mean, and $\hat{Q} = \sum(1 - e^{-L_i/\hat{\theta}})$.

This is a single arm phase two study. Patients will be accrued uniformly over two years, and then followed for two years. The power calculations are based on derivations from Lawless⁵³ with a cube-root transformation of the maximum likelihood estimate (MLE), as suggested by Spratt⁵⁴. This is implemented in the online calculator (tool of One Arm Survival) found at <https://stattools.crab.org> which is provided by the SWOG Statistical Center. Thus, 65 patients will give us at least 84% power to detect an effect size of 25% improvement in progression-free survival at 1 year compared to the estimated historical control rate, for varying proportions of patients with CLL and MCL. The following table reflects the power and effect size, if we enroll 65 patients with varying proportion of the diagnoses.

Table: Power achieved for a sample of 65 patients for different effect sizes using a 2-sided parametric test with level 0.05, assuming on 2 years of uniform accrual and 2 years of follow-up time.

	%CLL	%MCL	1 year PFS Historical Control	1 year PFS Treated	Power
20%	30	70	0.55	0.660	74
	40	60	0.56	0.672	76
	50	50	0.57	0.684	78
	60	40	0.58	0.696	80
	70	30	0.59	0.708	83
25%	30	70	0.55	0.688	91
	40	60	0.56	0.700	92
	50	50	0.57	0.713	93
	60	40	0.58	0.725	95
	70	30	0.59	0.738	96
30%	30	70	0.55	0.715	98
	40	60	0.56	0.728	98
	50	50	0.57	0.741	99
	60	40	0.58	0.754	99
	70	30	0.59	0.767	99

In addition, cohort B will include 10 patients (FL and HD). There is no formal sample calculation for cohort B.

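### Both mortality stopping tables end at 40 of 75 patients, and the plan does not say when a patient counts in a row

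*Combined protocol and SAP*

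**What the plan says.** Section 24.3 (Safety Analyses) puts both cohorts in the safety analyses: "Combining cohort, A and B with 75 patients in total, the stopping rules are created based on Bayesian approach". The trial stops early if the probability that treatment-related events on the regimen "exceeds conventional treatment related AE is greater than 80" per cent. The prior is not given.

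Two of the five limits concern death at 1 year after transplant (HCT):
- all-cause non-relapse mortality: "Cumulative incidence of non-relapse mortality (all cause) at 1 y post HCT should not be higher than 40" per cent;
- infectious mortality: "Cumulative incidence of infectious disease mortality (not related to GVHD) should not be higher than 30% at 1 y post HCT".

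Both tables have a column headed "Number of patients in complete cohorts of 5 (inclusive") with rows 5, 10, 15, 20, 25, 30, 35 and 40. Both print the same stopping counts: 4, 6, 8, 10, 13, 15, 17 and 19. Neither has a row beyond 40.

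On implementation the section says: "There will be 2 conference calls per month during the conduct of the study". It does not say whether a patient enters a row at registration, at transplant, at the first ibrutinib dose or after a year of follow-up.

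Section 24.2 (Sample Size) gives 65 patients in cohort A and 10 in cohort B. On accrual it says: "Patients will be accrued uniformly over two years, and then followed for two years".

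**The concern.** The GVHD tables are split by GVHD status before ibrutinib, so a shorter table could reflect a smaller subgroup. That does not explain the mortality tables, because every one of the 75 patients can die of infection or of a non-relapse cause. A rule stated for 75 patients is tabulated for 40, which leaves 35 (47%) without a boundary.

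The second gap is the counting rule. The limits are set at 1 year and the rows are complete cohorts of five. One reader could wait until the fifth patient has a full year of follow-up; another could count each death as it is reported. Both would be following the text, and they would stop at different times. In a single-arm trial these tables are the only formal mortality boundaries.

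**Working it through.** **1. Reproduce the printed NRM table.** The boundary at n patients is the smallest r with P(p > 0.40 | Beta(a + r, b + n − r)) > 0.80. The prior has to be assumed. Beta(0.4, 0.6) and Beta(0.8, 1.2), both with mean 0.40, each return all eight printed values. A Jeffreys prior gives 3 instead of 4 at n = 5. A uniform prior also gives 12 instead of 13 at n = 25. With Beta(0.8, 1.2) the posterior probability is 0.730 at 18/40 and 0.823 at 19/40, so 19 is the boundary.

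**2. Extend it.** Both matching priors give the same further rows:

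| n | 45 | 50 | 55 | 60 | 65 | 70 | 75 |
|---|---|---|---|---|---|---|---|
| stop at | 21 | 24 | 26 | 28 | 30 | 32 | 34 |

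**3. Chance of ever stopping on the NRM rule** (200,000 simulated trials; independent patients; deaths within 1 year):

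| True 1-year NRM | Printed (to 40) | Extended (to 75) |
|---|---|---|
| 40% (the limit) | 41% | 48% |
| 45% | 62% | 74% |
| 50% | 81% | 92% |

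**4. When rows mature if they wait for 1 year.** Assume the two-year uniform accrual applies to all 75 patients: 75/24 = 3.125 per month. Row k matures at k/3.125 + 12 months, with 3.125 times that many months enrolled, up to 75.
- Row 5: 5/3.125 + 12 = 13.6 months; 3.125 × 13.6 = 42.5, so 42 enrolled.
- Row 35: 23.2 months, 72 enrolled.
- Row 40: 40/3.125 + 12 = 24.8 months, 0.8 month after accrual closes.
- Added rows 45 to 75: 26.4 to 36.0 months.

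Sensitivity:
- A one-month lag from registration to transplant gives 45 enrolled at row 5 and month 25.8 for row 40.
- If only 60–80% of registered patients start ibrutinib and count (assumed range), row 5 falls at 43–45 enrolled and row 40 at months 28.0–33.3.
- If accrual takes 30 or 36 months, row 5 falls at 35 or 30 enrolled, and row 40 matures before closure.
- Row 40 matures after closure only if accrual of A months satisfies 40A/75 + 12 > A, that is A < 25.7.

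**5. Timing of stops at 50% NRM** (constant hazard of death over the first year, assumed):

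| | Rows wait 1 year | Deaths counted as they occur |
|---|---|---|
| Median stop, printed table, among trials that stop | month 15.2 (47 enrolled) | about month 12 (37–38 enrolled) |
| Stopped before month 24, printed | 77% | about 81% |
| Stopped before month 24, extended | 77% | about 84% |

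Of the 11-point gain from extension (81% to 92%), at most about 3 points fall before accrual closes.

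**6. The infectious-mortality table.** The same method at a 30% limit gives 3, 5, 7, 8, 10, 12, 13, 15 for rows 5 to 40. The first six match the plan's printed 30% GVHD table. The infectious table instead prints the 40% values. Extending it at 30% would put 17/45 after the printed 19/40: fewer deaths needed among more patients.

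**The case against.** The strongest reply concerns timing. A reader might infer that no stop is possible until 42 patients are enrolled, or that the rule comes too late to stop enrolment. The documents do not support either. Nothing in Section 24.3 says a row waits for follow-up. Calls are held twice a month, Section 25.2.2 makes every death a serious adverse event, and Section 25.11 requires reporting within 24 hours. Four deaths among the first five patients cross the first row when the fourth occurs. Counting that way at 50% NRM, just over half of trials stop before month 13.6. Even if rows wait, seven of the eight mature during accrual and 77% of trials stop before month 24. The statement that the last row matures after closure has a margin of 0.8 month, and it relies on an accrual sentence written for the 65-patient power calculation.

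It is also fair that the 80% rule in the text has no cut-off at 40, and that Section 26.8 gives the data and safety monitoring committee quarterly review of serious adverse events and authority to intervene. So patients 41–75 are not without oversight. What they lack is a tabulated boundary.

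These replies limit the timing point and the size of the benefit during accrual. They do not supply the missing rows or say when a patient counts.

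**Conclusion.** The omission stands: the rule is stated for 75 patients and both mortality tables end at 40. For NRM at a true rate of 50%, completing the table cuts the chance of never stopping from 19% to 8%. The price is 7 more points of stopping when the true rate equals the limit. Most of the benefit is to patients still on treatment or in follow-up after accrual closes; the effect on enrolment itself is small.

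The counting rule is unspecified, which is a narrower fault than a rule that cannot act. If rows waited a year, the median stop at 50% NRM would come about three months later than necessary, with roughly ten more patients enrolled.

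The boundary rows rest on an inferred prior, but both priors that reproduce the printed table agree. The dates rest on uniform 24-month accrual of all 75, and the as-they-occur figures also on a constant first-year hazard. The infectious-mortality table has a separate inconsistency with its own limit, so no extended rows are offered for it here.

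**What to change.** 1. Extend the NRM table with the plan's own 80% rule: 21/45, 24/50, 26/55, 28/60, 30/65, 32/70, 34/75. State the prior.
2. Reconcile the 30% infectious-mortality limit with the table printed under it, then extend that table to 75 by the same rule.
3. Define the safety denominator. State that at each twice-monthly call, qualifying deaths within 1 year of HCT among the first 5, 10, 15 and so on of those patients are compared with the row as they occur, without waiting for 1-year follow-up. Qualifying means non-relapse deaths for one table, and infectious deaths not related to GVHD for the other.

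The 1-year and cause restrictions in item 3 are essential. With them, the count in a fixed group can only rise towards its final value, so the decision is the same but sooner. Without the 1-year cap, year-2 deaths would be held against a 1-year boundary. If NRM rose from 40% at 1 year to 45–50% at 2 years (assumed range), the extended table would stop 74–92% of trials by the end of two-year follow-up, instead of 48%.

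The cost is longer tables, a few sentences, and the rise from 41% to 48% in stopping at the limit. The calls and death reporting already exist.

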24.4 Association Analyses with Correlative Studies

Appropriate methodologies for association analyses of immunoseqMRD,, IMMUNOSEQ, and CYTOF with relevant clinical variables will be undertaken.

25. SAFETY DATA COLLECTION AND REPORTING

25.1 Management of Safety Data

This Study has been designated as an interventional study. As such, all adverse events, special situations, including pregnancies and product quality complaints will be reported as described in this protocol from the time a subject has signed and dated an Informed Consent Form (ICF) until 30 days after the last documented use of a product under study within the study. All subsequent AEs and SAEs will be collected after this period if the Principal Investigator considers the AE/SAE to be causally-related to the use of the study drug.

For the purposes of this study, the J&J medicinal product is: Ibrutinib (Imbruvica).

The safety variables to be analyzed include adverse events, clinical laboratory test results (hematology and chemistry), and other safety measurements. They will be summarized by descriptive statistics. In general, continuous variables will be summarized using descriptive statistics (n, mean, median, standard deviation, standard error and range). Categorical variables will be summarized using frequencies and percentages. No formal statistical testing is planned. Exposure to ibrutinib first dose and reasons for discontinuation from study treatment will be tabulated.

